## **2-Materials and Methods**

### **2-1 Study design**

This is a cross-sectional observational study that was conducted between January and May 2025 in Al-Anbar Oncology Centre, Al-Anbar, Iraq.

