## **2-6 Data Analysis**

Data was analyzed using IBM SPSS Statistics version 26. Descriptive statistics (mean, standard deviation, frequency, and percentage) were used to summarize demographic and clinical variables. The Kolmogorov-Smirnov test was applied to assess the normality of continuous variables, and due to non-normal distribution, non-parametric tests were used.

Bivariate analyses included Spearman's correlation coefficient to evaluate associations between psychological outcomes (depression, anxiety, stress) and continuous predictors such as sleep quality, cost, and number of children. The Kruskal-Wallis H test was employed to examine differences in distress levels across cancer stages.

Categorical associations were evaluated using Pearson's Chi-square test. Binary logistic regression analysis was conducted to identify predictors of severe anxiety. Additionally, multivariate linear regression models were constructed for each psychological outcome (PHQ-9, GAD-7, stress), and multicollinearity was assessed using the Variance Inflation Factor(VIF).

Receiver Operating Characteristic (ROC) curve analysis was used to assess the predictive accuracy of stress scores for severe anxiety, with Area Under the Curve (AUC) interpreted based on conventional thresholds. Conceptual path modeling was used to explore potential indirect relationships between stress and anxiety, mediated by sleep disturbance and impaired daily performance.

All tests were two-tailed, and a p-value of less than 0.05 was considered statistically significant.

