### 3 - Results

A total of 500 breast cancer patients were included in the final analysis. Descriptive statistics revealed a high prevalence of psychological distress within the sample, with elevated scores in depression, anxiety, and stress domains.

Spearman correlation analysis revealed strong positive associations between sleep difficulty and psychological outcomes: depression ( $r = 0.85$ ), anxiety ( $r = 0.77$ ), and stress ( $r = 0.85$ ), all statistically significant at  $p < 0.001$ . Use of sedatives was also significantly correlated with elevated distress scores ( $r > 0.90$  across models).

Kruskal-Wallis tests demonstrated statistically significant differences in mean ranks of depression, anxiety, and stress across cancer stages ( $p < 0.01$ ), with higher distress in patients with advanced-stage disease.

Multivariate linear regression identified the following as significant predictors of psychological distress:

- PHQ9\_Total:  $\beta = 0.42$ ,  $p < 0.001$
- Anger:  $\beta = 2.08$ ,  $p < 0.001$
- Cancer Stage:  $\beta = 0.92$ ,  $p = 0.0014$

Psychological support was not a significant predictor ( $p = 0.606$ ).

Binary logistic regression showed that PHQ9 and anger significantly predicted severe anxiety, with odds ratios of 1.32 and 1.27, respectively ( $p < 0.001$ ). Stage of disease also emerged as a significant factor in anxiety prediction.

Receiver Operating Characteristic (ROC) curve analysis yielded an Area Under the Curve (AUC) of 0.74 for stress in predicting severe anxiety, indicating a fair level of discriminative ability.

Finally, conceptual path analysis demonstrated that the relationship between stress and anxiety was primarily indirect, mediated through sleep disturbance and daily performance impairment. The direct path from stress to anxiety was negligible ( $r = -0.01$ ), suggesting a mediated mechanism of action.

**Table 1.** Descriptive Statistics of Study Variables

Variable	N	Minimum	Maximum	Mean	SD
Total Cost	500	80	34785	3721.69	4456.79
PHQ9_Total	500	1	27	17.99	6.11
GAD7_Total	500	1	21	12.79	3.81
Cancer Stage	500	0	4	2.52	1.09
Children	500	0	5	2.53	1.63
Metastatic	500	0	1	0.36	0.48
Stress Level	500	0	4	2.64	0.79

The descriptive characteristics of the study variables are presented in **Table 1**. Depression and anxiety scores were moderately high, while stress levels were also elevated. Treatment cost showed substantial variability across participants.

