**Table 5:** Binary Logistic Regression – Predicting Severe Anxiety

Predictor	Odds Ratio (OR)	95% CI	P-value
Depression (PHQ-9)	1.32	1.18 – 1.56	<0.001

Anger	1.27	1.11 – 1.49	0.002
Stress Level	1.14	1.03 – 1.35	0.017
Psychological Support	0.54	0.33 – 0.91	0.021
Cancer Stage	0.61	0.33 – 0.87	0.049

[figure not shown]
Binary logistic regression (**Table 5**) showed that depression, anger, and stress significantly increased the odds of severe anxiety, while psychological support and advanced cancer stage were protective. The corrected model (**Table 6**) confirmed these associations.

**Table 6.** Logistic Regression Predicting Severe Anxiety (Corrected Model)

Predictor	Coef. ( $\beta$ )	Std. Error	z-value	p-value	95% CI (Lower – Upper)
PHQ9_Total	0.42	0.06	6.92	<0.001	0.30 – 0.53
Anger	2.08	0.48	4.36	<0.001	1.14 – 3.02
Psych Support	-0.18	0.34	-0.52	0.606	-0.84 – 0.49
Cancer Stage	0.92	0.29	3.20	0.0014	0.36 – 1.48

[figure not shown]
This table presents the corrected logistic regression model for predicting severe anxiety. PHQ9\_Total and anger were significant positive predictors, while psychological support did not show a significant protective effect in the adjusted model.

**Figure 2.** ROC Curve for stress predicting severe anxiety.

The ROC curve (**Figure 2**) illustrates the predictive value of stress scores for severe anxiety, with an AUC of 0.74 ( $p < 0.001$ ), indicating fair discriminative accuracy.

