Furthermore, Kruskal-Wallis analysis confirmed significant differences in mean ranks of depression, anxiety, and stress across cancer stages ( $H = 14.76$  to  $31.09$ ,  $p < 0.01$ ). These findings are supported by evidence from Iran and neighboring countries, where patients with stage III and IV breast cancer reported higher rates of emotional distress compared to the early stages of the disease (14). The increased psychological vulnerability in advanced stages underscores the need for stage-specific psychosocial interventions in cancer care protocols

Interestingly, total treatment cost showed a weak but statistically significant inverse correlation with psychological distress variables (e.g., PHQ-9\_Total:  $r = -0.11$ ,  $p = 0.017$ ). Although initially counterintuitive, this finding may reflect a perceived sense of security or access to higher-quality care among patients with greater financial capacity. Similar interpretations were reported in recent findings from Turkey, where patients with access to private sector services and higher financial resources exhibited lower levels of psychological distress despite elevated treatment costs, suggesting that financial ability may buffer emotional burden through enhanced control and perceived care quality (17).

As for psychological support, logistic regression models from this study suggested a protective effect ( $OR = 0.54$ ), though this was not statistically significant in the adjusted model ( $p = 0.606$ ). The lack of significance may be attributed to limited availability or underutilization of structured psychological services in the region, a challenge frequently reported in Iraq and across low-resource Middle Eastern settings. (18,19). Nonetheless, the direction of effect emphasizes the urgent need to integrate psychosocial support into routine oncology care.

Among all predictors examined, depression (PHQ9\_Total) and anger emerged as the strongest independent predictors of severe anxiety in both logistic and linear regression models ( $\beta = 0.42$  and  $2.08$ , respectively,  $p < 0.001$ ). These findings support prior research indicating that depressive symptomatology often precedes or co-occurs with anxiety in cancer patients, especially when emotional regulation is compromised (11)

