Although anger remains an underexplored emotional construct in oncology, its relevance is gaining traction. In Iraq, sociocultural norms that discourage emotional expression, combined with the psychological toll of cancer, may intensify internalized anger, contributing to emotional dysregulation. This perspective is supported by findings from the national report, which highlighted elevated psychological distress among cancer patients and emphasized the role of suppressed emotions in shaping anxiety and avoidance behaviors (20).

These findings emphasize the significance of addressing emotional dysregulation, particularly in patients presenting with overlapping symptoms of depression and anxiety.

This suggests that psychological screening tools should incorporate anger-related items to facilitate the early identification of high-risk cases.

The conceptual path model derived from the dataset suggests that stress influences anxiety primarily through indirect mechanisms, notably sleep disturbance and impaired daily functioning. While the direct association between stress and anxiety was minimal ( $r = -0.01$ ), robust indirect effects were observed via sleep problems ( $r = 0.74$ ) and functional impairment ( $r = 0.77$ ). These findings are consistent with regional studies from Egypt and Oman, highlighting sleep disturbance and fatigue as key mediators of psychological distress in oncology patients. (Al-Habsi et al., 2021; Gabra & Hashem, 2021; Hendy et al., 2025).

This structure reinforces theoretical frameworks such as the Transactional Model of Stress and Coping, where maladaptive emotional responses (e.g., stress) translate into clinical outcomes (e.g., anxiety) through sleep and functional capacity mediators. Similar models have been proposed in Jordanian studies (24). Though the present model uniquely incorporates performance and anger as variables of interest, adding depth to the psychosocial profile.

The inclusion of psychological support and its weak inverse association with anxiety ( $r = -0.07$ ) further suggests that strengthening emotional resources could buffer the transition from stress to anxiety. This model may therefore serve as a foundational structure for targeted interventions in Iraqi cancer care systems, particularly in resource-limited settings.

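### The advice to add anger items to screening for early case-finding rests only on a concurrent association that two models report very differently; discrimination was measured for stress alone

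*Combined protocol and SAP*

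**What the plan says.** **Recommendation.** Section 4 (Discussion) states that "psychological screening tools should incorporate anger-related items to facilitate the early identification of high-risk cases". Shortly before, the same section says that "depression (PHQ9\_Total) and anger emerged as the strongest independent predictors of severe anxiety" and attributes this to both the logistic and the linear models.

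**Design.** Section 2-1: "This is a cross-sectional observational study that was conducted between January and May 2025". No follow-up is described.

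**Discrimination analysis.** Section 2-6: "Receiver Operating Characteristic (ROC) curve analysis was used to assess the predictive accuracy of stress scores for severe anxiety". Section 3 reports an "Area Under the Curve (AUC) of 0.74 for stress in predicting severe anxiety", and Figure 2 is for the same variable. No other ROC analysis is planned or reported.

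**Evidence on anger.** Anger appears in Table 5 and in Table 6, the table labelled as the corrected model. Both are logistic models of severe anxiety, and both include PHQ-9.

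**Measurement.** Section 2-4 describes PHQ-9 and GAD-7 and defines severe anxiety as a GAD-7 total of 15 to 21. It describes no anger instrument, and Table 1 has no row for anger.

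**The concern.** The sentence on anger is advice about screening practice, and it makes two claims: that anger items help to pick out high-risk patients, and that they do so early. The first needs evidence on classification, in particular what anger adds once a score such as PHQ-9 is known. The second needs an outcome that comes later than the marker. The study offers neither. Its one classification analysis concerns a different variable, and its outcome is a current GAD-7 score.

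A significant adjusted coefficient shows association. It does not say how many patients would be classified better. A centre acting on the sentence would lengthen its screening tool without knowing the gain, or even which anger items were used. The association itself is reported at two very different sizes.

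**Working it through.** **1. Anger in Table 6, reproduced.** Inputs: coefficient 2.08, SE 0.48, z 4.36, 95% CI 1.14 to 3.02.
- z = 2.08 / 0.48 = 4.33, which agrees with 4.36 within rounding of the inputs.
- CI = 2.08 ± 1.96 × 0.48 = 1.14 to 3.02, as printed.
- Odds ratio = exp(2.08) = 8.0, with limits exp(1.14) = 3.1 and exp(3.02) = 20.5.

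**2. Anger in Tables 5 and 6, side by side.**

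| | Odds ratio | 95% CI | Log odds ratio |
|---|---|---|---|
| Table 5 | 1.27 | 1.11 to 1.49 | ln(1.27) = 0.24 |
| Table 6 | 8.0 | 3.1 to 20.5 | 2.08 |

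The upper limit in Table 5 (1.49) lies below the lower limit in Table 6 (3.1). On the log scale the estimates differ by a factor of 2.08 / 0.24, or about 8.7. Table 5 also contains stress and Table 6 does not. The documents do not say whether that, a different coding of anger, or an error explains the gap. The direction is the same in both.

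**3. Linear models.** Table 4 holds the linear models for PHQ-9, GAD-7 and stress, and anger is in none of them. The value 2.08 listed in section 3 under linear regression is the logistic coefficient of Table 6. No separate linear estimate for anger can be found, so the statement that linear models support it has no visible source.

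**4. Discrimination reported.**

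| Marker for severe anxiety | AUC | Cut-off, sensitivity, specificity |
|---|---|---|
| Stress | 0.74 | none |
| PHQ-9 | none | none |
| PHQ-9 plus anger | none | none |
| Anger | none | none |

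No AUC for anger, and no change in AUC, can be derived from the published figures.

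**5. Precision of the one AUC.** The text gives no confidence interval and no count of severe cases. With A = 0.74, a = A/(2 − A) = 0.587 and b = 2A²/(1 + A) = 0.629, the Hanley-McNeil formula is

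SE² = [A(1 − A) + (n₁ − 1)(a − A²) + (n₀ − 1)(b − A²)] / (n₁n₀).

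The number of severe cases n₁ is an assumption:
- 10% of 500 (50 and 450): SE 0.042, CI 0.66 to 0.82.
- 50% of 500 (250 and 250): SE 0.022, CI 0.70 to 0.78.

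**6. Sample size.** 1.96² × 0.25 / 0.05² = 384.2, which reproduces the stated 384. This is a precision calculation for a prevalence. It says nothing about power to detect a gain in discrimination.

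**7. Which test for the added value.** A DeLong comparison of PHQ-9 with PHQ-9 plus anger, fitted to the same data, is badly conservative. An illustrative simulation used n = 500 and 1,000 runs. It assumed about 31% with severe anxiety, a binary marker present in 40%, and a normally distributed PHQ-like score. With no true effect, DeLong rejected in 0.0% of runs and the Wald test in 4.4%. With a true log odds ratio of 0.8, they rejected in 25% and 91%. DeLong should therefore not decide whether the recommendation stays.

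**The case against.** The strongest defence is that anger was tested. It is significant in two models that contain PHQ-9, which is evidence that it carries information beyond PHQ-9. This stands. A reader might infer that the recommendation has no supporting analysis at all; Tables 5 and 6 do not allow that reading. What they leave open is the size of any gain in classification, and they do not agree on the size of the association.

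Second, screening accuracy is normally judged against a concurrent reference standard, and GAD-7 defines the outcome here, so no marker in this dataset could outperform it. This also stands. Absence of follow-up does not invalidate a concurrent ROC. It does rule out the claim about early detection.

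Third, the stress ROC is not cited in support of anger, and the sentence on anger is worded as a suggestion and is not repeated in sections 5 or 6. Both are true, and they limit the weight of the point. The sentence remains advice on practice that a reader could follow.

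Three further inferences go beyond the documents:
- That stress, anger, PHQ-9 and GAD-7 came from one questionnaire. How stress and anger were collected is not stated; only the cross-sectional design is.
- That the stress score allows at most four cut-points. This assumes integer scoring, and Table 1 gives only a range of 0 to 4.
- That the ROC was run on a weaker marker than PHQ-9. Table 2 correlates PHQ-9 (0.79) and stress (0.65) with total GAD-7, which is not discrimination at 15 or above.

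**Conclusion.** The point holds in a limited form. Anger's concurrent association with severe anxiety, adjusted for PHQ-9, was tested and is positive in both models. Its value for screening was not: no discrimination measure exists for anger, alone or added to PHQ-9, and the design cannot show early detection of any kind. The supporting association is also unsettled, at an odds ratio of 1.27 or about 8.0 with intervals that do not overlap, for a variable whose measurement is not described.

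The conclusion needs no assumption about the data. It rests on what the report contains and on the printed coefficients. Only the AUC intervals and the DeLong simulation use assumed inputs, and both are illustrative. No reported estimate changes; what changes is the conclusion that can be drawn about anger in screening.

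**What to change.** **Wording (section 4).** Remove the claim of early detection. State the anger result as a concurrent association, and give its use in screening as a hypothesis for a prospective accuracy study. Remove the reference to linear models unless one containing anger is reported.

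**Wording (sections 2-6 and 3, Figure 2).** Describe the ROC as concurrent discrimination, not as predictive accuracy.

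**Before any screening recommendation.** State how anger was measured and coded. Reconcile the anger estimates in Tables 5 and 6, and say which model stands.

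**Analysis, on data already held.** Report the number with severe anxiety, and AUCs with 95% CI for PHQ-9, PHQ-9 plus anger, and stress. Give the change in AUC from adding anger with an optimism-corrected bootstrap interval, and test anger with a likelihood-ratio test, not DeLong.

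**Cost.** A little extra analysis, some edits, and no new data. The downside is a weaker recommendation.

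### The path model's 0.74 and 0.77 cannot both be indirect effects of stress on anxiety as labelled, and a cross-sectional study cannot demonstrate mediation

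*Combined protocol and SAP*

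**What the plan says.** Section 2-6 (Data Analysis) plans the path model as an exploration of possible indirect links from stress to anxiety, through sleep and daily performance. Section 2-1 describes the study as cross-sectional and observational.

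The Results go further: "conceptual path analysis demonstrated that the relationship between stress and anxiety was primarily indirect, mediated through sleep disturbance and daily performance impairment". They add: "The direct path from stress to anxiety was negligible" (r = −0.01), and close by inferring a mediated mechanism.

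The Discussion states: "The conceptual path model derived from the dataset suggests that stress influences anxiety primarily through indirect mechanisms, notably sleep disturbance and impaired daily functioning". On the mediated part it reports that "robust indirect effects were observed via sleep problems", giving 0.74 for sleep and 0.77 for function, both written as r. On the direct part its words are: "While the direct association between stress and anxiety was minimal", and the value given is r = −0.01. It places further variables in the model: "the present model uniquely incorporates performance and anger as variables of interest", and "The inclusion of psychological support and its weak inverse association with anxiety" (r = −0.07). It then proposes a use: "This model may therefore serve as a foundational structure for targeted interventions in Iraqi cancer care systems".

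The text under Figure 3 says that the figure carries β coefficients, whereas the Results and Discussion print r. Table 2 gives a Spearman correlation of 0.65 between Stress Level and GAD7_Total.

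**The concern.** There are two separate problems.

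**Labels.** An indirect effect is the part of the total effect that runs through a mediator: the product of the stress-to-mediator path (a) and the mediator-to-anxiety path (b). Direct and indirect parts must add to the model's total. Two indirect parts of 0.74 and 0.77 with almost no direct part are far too large for a stress–anxiety correlation of 0.65. The −0.01 also needs explaining: it cannot be a plain correlation, because that is 0.65, so it must be an adjusted coefficient. The available text does not say which sleep variable was adjusted for.

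**Interpretation.** Data from a cross-sectional study do not establish the order stress, then sleep and performance, then anxiety. The Results nevertheless report mediation as demonstrated.

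At stake is how a reader uses the model. Someone designing an intervention on the strength of the Discussion could take 0.74 and 0.77 as the sizes of two causal pathways.

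**Working it through.** **Inputs.** From the Discussion: direct −0.01, indirect 0.74 and 0.77. From Table 2 (Spearman): stress–GAD-7 0.65; stress–Sleep Difficulty 0.85; stress–Sleep Satisfaction 0.55; GAD-7–Sleep Difficulty 0.77; GAD-7–Sleep Satisfaction 0.62; Sleep Difficulty–Sleep Satisfaction 0.48. n = 500. I assume that stress and anxiety in the path model are Stress Level and GAD7_Total.

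**Step 1: the stated figures as labelled.** Total = direct + sum of indirect effects = −0.01 + 0.74 + 0.77 = 1.50. Allowing for rounding, the minimum is −0.015 + 0.735 + 0.765 = 1.485. With a total of 0.65, the direct path would have to be 0.65 − 1.51 = −0.86.

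**Step 2: could other variables in the model explain 1.50?** With covariates, the total need not equal 0.65. But the semipartial correlation, β × √(1 − R²), cannot exceed 1, where R² is the share of the variance of stress explained by the covariates. So β = 1.50 needs R² ≥ 1 − 1/1.50² = 1 − 1/2.25 = 0.556, even if the model explained anxiety perfectly. With 1.485 the bound is 1 − 1/2.205 = 0.547. An unreported negative path of about 0.65 − 1.50 = −0.85 could also reconcile the sum with 0.65. None is reported; the only other figure given for the model is −0.07 for psychological support.

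**Step 3: what Table 2 gives for the direct path.** For one mediator:
- direct = (r_SA − r_SM × r_MA) / (1 − r_SM²)
- b = (r_MA − r_SM × r_SA) / (1 − r_SM²)
- indirect = r_SM × b

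*Sleep Difficulty:* direct = (0.65 − 0.85 × 0.77) / (1 − 0.85²) = −0.0045 / 0.2775 = −0.016. b = (0.77 − 0.85 × 0.65) / 0.2775 = 0.784. Indirect = 0.85 × 0.784 = 0.666. Sum 0.65.

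*Sleep Satisfaction:* direct = (0.65 − 0.55 × 0.62) / (1 − 0.55²) = 0.309 / 0.6975 = +0.443. b = (0.62 − 0.55 × 0.65) / 0.6975 = 0.376. Indirect = 0.55 × 0.376 = 0.207, which is 32% of 0.65.

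*Both together* (standardised regression of GAD-7 on stress and both sleep variables): direct = −0.202. Indirect = 0.652 + 0.199 = 0.852 before rounding of the parts. Sum 0.65.

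| Sleep variable | Direct | Approx. 95% CI | Range from rounding of inputs | Indirect |
|---|---|---|---|---|
| Sleep Difficulty | −0.016 | −0.12 to 0.09 | −0.07 to +0.03 | 0.67 |
| Sleep Satisfaction | +0.44 | 0.37 to 0.52 | 0.43 to 0.46 | 0.21 |
| Both | −0.20 | −0.30 to −0.10 | −0.28 to −0.13 | 0.85 |

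The intervals use ordinary least-squares standard errors (0.054, 0.037, 0.050), which are approximate for ranks. These rows are illustrations, not estimates of the authors' model, because daily performance, anger and psychological support are not in Table 2. The third sleep variable, Sleep-related Worry (Table 4), is not there either.

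So the reported −0.01 agrees with adjustment for Sleep Difficulty. The other two choices give clearly different values, and rounding does not account for the differences.

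**Step 4: the wording set against the design.** Section 2-1 gives a cross-sectional design and section 2-6 an exploratory aim. The Results report mediation as demonstrated. Models with anxiety disturbing sleep and raising stress, or with a common cause of all of them, can fit the same correlations. The available text gives no confidence interval or test for any indirect effect.

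**The case against.** **A reader might infer that no reading of the three figures can be reconciled with Table 2.** The documents do not support that. The 0.65 is a Spearman correlation; the scale of the path model is not stated, and with anger and psychological support included its total need not be 0.65. Two separate one-mediator models with a total of 0.65 would need direct paths of 0.65 − 0.74 = −0.09 and 0.65 − 0.77 = −0.12. A two-leg product gives 0.74 × 0.77 − 0.01 = 0.56. These miss the reported values by only about 0.1, too little to exclude such readings on an uncertain benchmark. A chain from stress through sleep and function to anxiety also has three legs, so two figures do not define it. Only the additive reading is clearly excluded. If the figures are legs of a chain, however, they are still not indirect effects, and the label remains wrong.

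**A reader might also infer that the −0.01, or the claim that the association is mainly indirect, is false.** That is not shown. Sleep Difficulty is the natural reading of sleep disturbance, and it gives −0.016. With both sleep variables the association is still mainly indirect; only the description of the direct path as negligible fails. The claim reverses only with Sleep Satisfaction alone, a less natural choice. Figure 3 may name the variable and mark 0.74 and 0.77 as single paths. Not naming the sleep scale in the text is, by itself, missing detail.

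**On wording,** section 2-6 and much of the Discussion are hedged. The overstatement lies mainly in the Results, in the verb *demonstrated*. That objection stands, and it narrows the correction needed.

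**Conclusion.** The point holds as a labelling error and a causal-wording error in a secondary, exploratory analysis.

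- As additive standardised effects, the stated figures total 1.50 against a stress–GAD-7 correlation of 0.65. A total of 1.50 would need covariates explaining at least 56% of the variance of stress. The 1.50 estimates nothing; it shows that the label cannot be right. That the values are single paths or simple correlations is an inference, because Figure 3 is not shown in the copy reviewed and the symbols r and β are mixed.
- The −0.01 is plausible as a coefficient adjusted for Sleep Difficulty, but its meaning depends on a variable that the available text does not name.
- The statement that mediation was demonstrated exceeds both the cross-sectional design and the exploratory aim in section 2-6.

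It would be wrong to infer that the study's main message falls. Section 6 (Conclusion) reports associations with sleep, sedative use, stage and emotional dysregulation and does not rest on the path model. Section 5 (Clinical Implications) likewise cites associations. This should be fixed, but it does not undermine the study as a whole.

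**What to change.** On the existing 500 records:

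1. Name the sleep variable and the daily-performance variable used in the path model, and state whether anger and psychological support are mediators or covariates.
2. Report the total effect, the direct effect and each a × b indirect effect on one scale with bootstrap 95% CIs. Check that the parts sum to the model's own total.
3. Replace or relabel 0.74, 0.77 and −0.01 in the Results and Discussion, using one symbol that matches Figure 3.
4. In the Results, replace *demonstrated* and the closing inference of a mediated mechanism with *is consistent with*, and add that reverse order or a common cause cannot be excluded. The wording already hedged in the Discussion needs little change.
5. Mark the Discussion sentence that offers the model as a basis for interventions as hypothesis-generating.

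The cost is a short reanalysis and a softer secondary conclusion. No new data are needed, and the change of verb in item 4 and the marking in item 5 need no reanalysis.

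### The Discussion infers that psychological support could buffer the step from stress to anxiety, but no stress-by-support interaction is planned or reported, and the one figure cited carries no p-value or confidence interval.

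*Combined protocol and SAP*

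**What the plan says.** In the part of section 4 (Discussion) that deals with the path model, psychological support is described as having a weak inverse association with anxiety, r = -0.07. The text says this "further suggests that strengthening emotional resources could buffer the transition from stress to anxiety". It gives no p-value or interval and does not say what kind of coefficient r is. The next sentence offers the model as a basis for targeted interventions in Iraqi cancer care.

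The analyses that could bear on this are set out in section 2-6 (Data Analysis):

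- Correlations: "Bivariate analyses included Spearman's correlation coefficient to evaluate associations between psychological outcomes" and continuous predictors.
- Path model: "Conceptual path modeling was used to explore potential indirect relationships between stress and anxiety, mediated by sleep disturbance and impaired daily performance".
- Significance rule: "All tests were two-tailed, and a p-value of less than 0.05 was considered statistically significant".

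Section 3 (Results) states that "A total of 500 breast cancer patients were included in the final analysis". Psychological support appears in two of its regression tables. Table 5 gives an odds ratio for severe anxiety of 0.54 (95% CI 0.33 to 0.91, p = 0.021). Table 6, labelled the corrected model, gives a coefficient of -0.18 (SE 0.34, 95% CI -0.84 to 0.49, p = 0.606). The comment under Table 6 is that "psychological support did not show a significant protective effect in the adjusted model".

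**The concern.** To say that support buffers the passage from stress to anxiety is to say that support changes the strength of the stress-anxiety relation. That is moderation. An association between support and anxiety is a different quantity: it can be present with no moderation, and moderation can be present when it is close to zero. So r = -0.07 could not establish buffering even with a small p-value, and the text gives it no p-value.

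At stake is what the study may conclude about support. A reader planning services could take the sentence as evidence that adding support would weaken the effect of stress, and it stands directly before the suggestion that the model can guide interventions.

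**Working it through.** **1. Is there a test of buffering?** For anxiety score A, stress S and support P, the model needed is

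A = b0 + b1·S + b2·P + b3·(S×P) + covariates.

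The stress slope is b1 + b3·P. Buffering means that b3 moves this slope towards zero as support increases. The places where b3 could appear are:

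- Section 2-6: correlations, Kruskal-Wallis, chi-square, linear and logistic regression, ROC and a mediation-type path model. No interaction or moderation analysis is listed.
- Table 4, GAD-7 model: sedatives, sleep-related worry, sleep satisfaction, children, cost and metastatic status. Neither S nor P is in it.
- Table 5: S and P as separate main effects, with no product.
- Table 6: P but not S, and no product.
- Figure 3: the drawing is not available. Its caption and the surrounding text describe only mediation by sleep and daily functioning.

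No estimate of b3 is reported, so no size for buffering can be computed.

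**2. What does r = -0.07 show?** Inputs: r from the Discussion, n = 500 from Results, two-sided 0.05 from section 2-6. Formula: t = r·√((n−2)/(1−r²)) on n−2 degrees of freedom.

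*Check on a figure the documents state.* The Discussion reports r = -0.11, p = 0.017 for total cost against PHQ-9. The formula gives t = -2.47, p = 0.014. Over the rounding range -0.105 to -0.115, p runs from 0.019 to 0.010. The stated 0.017 lies inside that range, so the formula reproduces it.

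*Applied to support, if r is a zero-order correlation on all 500 patients:*

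- t = -0.07·√(498/(1−0.0049)) = -1.57, p = 0.118.
- Rounding range -0.065 to -0.075: p = 0.147 to 0.094.
- Fisher z: -0.0701 ± 1.96/√497 = -0.0701 ± 0.0879, which transforms back to a 95% CI of -0.157 to 0.018.
- The smallest |r| that reaches p < 0.05 at n = 500 is 0.088.

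*If r is a path coefficient,* none of this applies, and the documents give no standard error from which to test it. There is reason to doubt the zero-order reading. The same part of the Discussion gives r = -0.01 for the direct stress-anxiety association, whereas Table 2 gives a Spearman correlation of 0.65 between stress and GAD-7. The Figure 3 caption also refers to β coefficients.

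**3. Is the main effect of support settled?**

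- Table 5: the SE from the interval is (ln 0.91 − ln 0.33)/3.92 = 0.259. Then z = ln 0.54/0.259 = -2.38, p about 0.017, close to the stated 0.021.
- Table 6: -0.18/0.34 = -0.53, p = 0.597. Rounding of the inputs allows up to about 0.61, so 0.606 is reproduced. As an odds ratio this is exp(-0.18) = 0.84, with 95% CI exp(-0.84) to exp(0.49) = 0.43 to 1.63.

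Each table broadly agrees with itself, but the two lead to opposite conclusions about the same predictor.

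**The case against.** The sentence is hedged, and the documents already say in Results and Discussion that support was not significant in the adjusted model. The verb may also be loose: elsewhere the Discussion uses it of financial ability easing emotional burden. These points lower the weight of the matter. They do not supply the missing test, because a cautious sentence about moderation still needs some estimate of moderation. If only a protective main effect was meant, the evidence is r = -0.07 without a test and two tables that disagree.

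Three stronger readings are tempting, and the documents do not support them.

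- *That r = -0.07 is simply non-significant.* This follows only if it is a zero-order correlation on all 500 patients, which is doubtful for the reasons shown in the working.
- *That support has no association with anxiety.* Table 5 gives a nominally significant protective odds ratio. The corrected Table 6 does not confirm it, but its interval of 0.43 to 1.63 leaves room for an effect in either direction. A null interaction would not settle this either.
- *That the study's recommendations rest on buffering.* The remark about targeted interventions refers to the whole path model, which is mainly about mediation. Sections 5 and 6 rest on sleep, sedative use, stage and emotional dysregulation, and neither mentions buffering.

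**Conclusion.** The concern holds as stated in the heading. The buffering claim is untested: no stress-by-support term is planned in section 2-6 or reported in Tables 4 to 6. This part rests only on reading the documents, with the caveat that the Figure 3 drawing could not be inspected.

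The cited r = -0.07 does not fill the gap. On the zero-order assumption, p is about 0.12 (0.09 to 0.15 over rounding), with a 95% CI of -0.16 to 0.02. On the path-coefficient assumption, no test is given. The main effect of support is unresolved between Table 5 and Table 6. The documents do not show that buffering is absent, only that nothing reported bears on it.

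This is a secondary claim, but it should be corrected because it stands next to advice on interventions and can be corrected cheaply.

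**What to change.** 1. Fit a linear model for GAD-7 and a logistic model for severe anxiety, each containing stress, support and their product, and report the product with its 95% CI. This adds three terms to the Table 4 GAD-7 model, two to the Table 6 model and one to the Table 5 model. State how support is coded, since the sign of the product depends on it.
2. Keep the buffering sentence only if the interaction shows a weaker stress slope with support. Otherwise delete it and do not use it in support of targeted interventions. A null product should not be reported as evidence about the main effect.
3. State what r = -0.07 is (Spearman, Pearson or path coefficient) and give its p-value and CI.
4. Report the main effect of support as not established in the corrected model. Note the conflict between Tables 5 and 6 and reconcile them.

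The cost is a small reanalysis of data already held and a few sentences of text. The likely consequence is that one Discussion claim is withdrawn.
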